IAP	Integrated Analysis Plan
ICH	International Conference on Harmonization
IPD	Important Protocol Deviation
LLOQ	Lower Limit of Quantification
MedDRA	Medical Dictionary for Regulatory Activities
MW	Molecular Weight
NA	Not Applicable
NCA	Non-compartmental Analysis
PD	Protocol Deviation or Pharmacodynamics
PK	Pharmacokinetics
PKAS	Pharmacokinetic Analysis Set
PT	Preferred Term
Q1	25th percentile
Q3	75th percentile

SAE	Serious Adverse Event
SAF	Safety Analysis Set
SCR	Screening Analysis Set
SD	Standard Deviation
SDTM	Study Data Tabulation Model
SI	Système International
SOC	System Organ Class
TEAE	Treatment-Emergent Adverse Event
ULOQ	Upper Limit of Quantification
WHO-DD	World Health Organization Drug Dictionary

3 Modification History

Unique Identifier for Version	Date of IAP Version	Author	Changes from the Previous Version
1.0	06 October 2022	PPD	Initial version

4 Purpose of the Integrated Analysis Plan

The purpose of this IAP is to document technical and detailed specifications for the final analysis of data collected for protocol MS202359_0004. Results of the analyses described in this IAP will be included in the CSR. Additionally, the planned analyses identified in this IAP may be included in regulatory submissions or future manuscripts. Any post-hoc, or unplanned analyses performed to provide results for inclusion in the CSR but not identified in this prospective IAP will be clearly identified in the CSR.

The IAP is based upon Section 9 (Statistical considerations) of the study protocol and is prepared in compliance with ICH E9. It describes analyses planned in the protocol, with the exception of CCI analysis for the effect of CCI variants on the PK of xevinapant which will be described and reported separately.

The wording used in this IAP is chosen to best match the respective wording in the study protocol template, the Clinical Study Report (CSR) template, CDISC requirements and special requirements for table layouts. Therefore, the following approach is used:

Generally, the term ‘participant’ will be used instead of ‘subject’ or ‘patient’. However, in tables and listings the term ‘subject’ will be used to match CDISC requirements, except for in-text tables where ‘participant’ will be used to match the CSR and protocol templates. Similarly, the term ‘study intervention’ will be used in this document instead of ‘treatment’ to match protocol and CSR templates, however, tables and listings will use ‘treatment’ for brevity reasons. Exceptions from this rule are commonly used terms like “on-treatment”, “treatment-emergent”, “treatment policy”, “subject-years”, “by-subject”, or names of eCRF pages like “Treatment Termination” page.

5 Objectives and Endpoints

Objectives	Endpoints	IAP section
Primary		
To characterize the xevinapant PK after a single 200 mg dose in healthy East Asian participants and in healthy Japanese participants	Xevinapant AUC _{0-last} , AUC _{0-∞} , and C _{max}	16.1
Secondary		

Objectives	Endpoints	IAP section
To evaluate the safety and tolerability of a single 200 mg dose of xevinapant in healthy East Asian participants and in healthy Japanese participants	Occurrence of TEAEs (incidence, frequency, intensity and causality), occurrence of changes in safety laboratory assessments, 12-lead ECGs, and vital signs	15
To determine additional plasma PK parameters of xevinapant after a single 200 mg dose in healthy east Asian participants and in healthy Japanese participants	Xevinapant AUC ₀₋₂₄ , t _{max} , t _{1/2} , CL/F, and V _Z /F	16.1
To characterize the PK of metabolite D-1143-MET1 after a single 200 mg dose in healthy East Asian participants and in healthy Japanese participants	D-1143-MET1 AUC _{0-last} , AUC ₀₋₂₄ , AUC _{0-∞} , C _{max} , t _{max} , and t _{1/2} , D-1143-MET1/xevinapant molar ratio for AUC _{0-last} , AUC _{0-∞} , C _{max}	16.1

6 Overview of Planned Analyses

All final, planned analyses identified in the IAP will be performed only after the last participant has completed the last visit, i.e. Follow-up/Discontinuation visit with all study data in-house, all data queries resolved, and the database locked.

There are no planned formal interim analyses.

Statistical analyses will be performed on the basis of CDISC SDTM data. These SDTM data contain as clean as possible eCRF data as well as external data including pharmacokinetic data.

A data review meeting will be held prior to any database lock. In addition, no database can be locked until this IAP has been approved (except for emergency).

7 Changes to the Planned Analyses in the Clinical Study Protocol

There are no changes to the planned analyses in the clinical study protocol.

8 Analysis Sets and Subgroups

8.1 Definition of Analysis Sets

Screening Analysis Set (SCR)

The Screening Analysis Set includes all participants who provided signed informed consent, regardless of the participant's randomization and study intervention status in the study.

Safety Analysis Set (SAF)

The Safety Analysis Set will include all participants who were administered any dose of any study intervention. Analyses will consider participants as treated.

PK Analysis Set (PKAS)

The PK Analysis Set will consist of all participants, who receive at least one dose of study intervention, and provide at least one measurable postdose concentration. A measurement BLQ is considered a valid measurement. Participants will be analyzed according to the actual study intervention they received.

The following table summarizes the use of the analysis sets in the different analyses.

Analyses	Analysis Set	
	SAF	PKAS
Baseline Characteristics	✓	
Previous and Concomitant Therapies	✓	
Compliance and Exposure	✓	
Safety and Tolerability	✓	
PK		✓

8.2 Subgroup Definition and Parameterization

Not applicable.

9 General Specifications for Data Analyses

The results of this study will be reported using summary tables, figures, and data listings, as appropriate. All data will be summarized by ethnic group (Japanese, non-Japanese East Asian and overall) and/or scheduled time point, as applicable.

Listings

In the individual participant data listing all individual data will be listed as measured. Repeated and unscheduled measurements will be included in the listings. All listings will be sorted by treatment, ethnic group, subject ID, and/or nominal time point, as appropriate. Data which are measured before administration of the study intervention will be sorted by participant number and nominal time point (if appropriate).

Tables and Descriptive Statistics

All data will be summarized by ethnic group (Japanese, non-Japanese East Asian and overall), day, and/or nominal time point, as appropriate. Repeated and unscheduled measurements included in the listings will not be used for summaries, unless the repeated measurement was performed due to unreliable values/technical reasons, e.g., clotted samples.

Unless otherwise specified, continuous variables will be summarized using descriptive statistics, i.e. the number of participants with non-missing values (n), mean, standard deviation (SD), median, 25th percentile (Q1) and 75th percentile (Q3), minimum (Min), and maximum (Max).

Qualitative variables will be summarized by frequency counts and percentages. Unless otherwise stated the calculation of proportions will be based on the number of participants of the analysis set of interest. Therefore, counts of missing observations will be included in the denominator and presented as a separate category.

Study day 1 for this study is defined as the date of study intervention.

All analyses will be performed using SAS® Software version 9.4 or higher.

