### 1.3

### Schedule of Activities

Assessments & Procedures	Screening	Admission to CRU					SFU (Televisit)	Notes
Study Day	-28 to -3	-1	1	2	3	4 (EoT)	8 (-1 / +2 days)	
Written informed consent	X							Informed consent to be available before start of any study specific assessments.
Participants resident at CRU		X	X	X	X	X		Admission to CRU in the afternoon on Day -1 until discharge on Day 4 after completion of all study-related activities
Inclusion and exclusion criteria	X	X						Recheck clinical status before administration
Demography	X							Including age (year of birth), sex, race and ethnicity
Full physical examination	X	X				X		
Medical history	X							
Pregnancy test	X	X				X		Pregnancy test using serum (at Screening) and using urine (on Day -1 and End of Study), to confirm non-pregnant status (females only)
Follicle stimulating hormone	X							To confirm postmenopausal status (females only)
Serology	X							HIV, hepatitis B and C SARS-CoV-2
Drug and alcohol screen	X	X						
Clinical laboratory tests a	X	X	X	X		X		After at least 10 hours fasting, Day 1 sampling is predose
Safety 12-Lead ECG	X		X	X		X		Day 1: predose, 1 hour postdose, Day 2 (24 hours postdose), and Day 4 (72 hours postdose) (see Section 8.2.3 for further details)

Assessments & Procedures	Screening	Admission to CRU					SFU (Televisit)	Notes
		-1	1	2	3	4 (EoT)		
Study Day	-28 to -3	-1	1	2	3	4 (EoT)	8 (-1 / +2 days)	
Vital signs	X	X	X	X	X	X		Height and Weight to be collected at Screening only. Day 1: predose, 1, 2, 4, 12 hours; Day 2: 24 hours, Day 3: 48 hours, Day 4: 72 hours
CCI								
Study intervention			X					
AE & SAE review	X	X	X	X	X	X	X	
Concomitant medications review	X	X	X	X	X	X	X	
PK blood sampling (plasma)			X	X	X	X		Day 1: predose, and 0.25, 0.5, 1.0, 1.5, 2, 2.5, 3, 4, 6, 8, and 12 hours postdose; Day 2: 24 and 36 hours postdose; Day 3: 48 hours postdose, Day 4: 72 hours postdose. See Section 8.4 for collection windows and further details. The time and date of each collection to be recorded in eCRF.

aUrine samples will be collected at Screening and times of other clinical labs.

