### 8.2.3 Electrocardiograms

- Single 12-lead ECG will be obtained as outlined in the SoA using an ECG machine that automatically calculates the heart rate and measures PR, RR, QRS, QT, and QTcF intervals.
- Triplicate ECGs are required when abnormal ECG results are measured. If ECG parameters fall outside of clinical reference range, including QTcF > 450 ms, a repeat ECG is done. When triplicate ECGs are required, 3 individual ECG tracings will be obtained as closely as possible in succession, but no more than 2 minutes apart. The full set of triplicates will be completed in less than 4 minutes and will occur in a resting state without prior procedure such as blood draw. Triplicate measurements can be performed

based on Investigators discretion. When measured as triplicate, the average values will be considered. Additional ECGs during the course of the study will be at the discretion of the Investigator.

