9.1 Definition of Baseline and Change from Baseline

If not otherwise specified, ‘baseline’ refers to the last scheduled measurement before administration of the study intervention.

However, if a participant is missing the baseline collection, the previous non-missing evaluation could become the baseline value (e.g. from screening/admission). If no baseline or previous to baseline evaluations exist, then the baseline value will be treated as missing.

Change from baseline is calculated as post-baseline visit value - baseline value.

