15.5 Other Safety or Tolerability Evaluations

Safety ECG data will be summarized by ethnic group (Japanese, non-Japanese East Asian and overall) and time point using descriptive statistics for baseline (see definition in Section 9), each evaluation during the study, and change from baseline to each evaluation. Listing of safety ECG data will be provided.

A listing of meal details will be provided.

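### Does it need settling which ECG value enters the summary tables when a triplicate is taken?

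*SAP*

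**What the plan says.** **Collection.** Protocol 8.2.3 sets the default: "Single 12-lead ECG will be obtained as outlined in the SoA". The Schedule of Activities places these ECGs at Screening and then at "Day 1: predose, 1 hour postdose, Day 2 (24 hours postdose), and Day 4 (72 hours postdose"). A triplicate is required when a result is abnormal and is otherwise at the investigator's discretion. The same section says: "If ECG parameters fall outside of clinical reference range, including QTcF > 450 ms, a repeat ECG is done". On the value to use it says: "When measured as triplicate, the average values will be considered". It does not say for what purpose, or whether the tracing that prompted the triplicate is one of the three.

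**Analysis.** Protocol 9.4.2 plans descriptive summaries of absolute ECG values and changes from baseline, with no replicate rule. SAP 9 (Tables and Descriptive Statistics) says: "Repeated and unscheduled measurements included in the listings will not be used for summaries". The one exception is a repeat made for technical reasons or because the value was unreliable. SAP 9.1 says baseline "refers to the last scheduled measurement before administration of the study intervention". SAP 15.5 begins "Safety ECG data will be summarized by ethnic group" and refers back to Section 9 for baseline, without mentioning triplicates. SAP 7 says: "There are no changes to the planned analyses in the clinical study protocol".

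**The concern.** A triplicate prompted by a QTcF above 450 ms is a repeat for abnormality, not for a technical fault, so the SAP 9 exception does not cover it. SAP 9 then keeps the first reading, while the protocol sentence seems to point to the average. If the protocol sentence governs the tables, SAP 9 would depart from it without SAP 7 saying so.

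A programmer could in principle use any of three values: the first reading, the mean of three new tracings, or the mean of the first reading and two more. The choice can matter for one participant. With invented tracings of 456, 446 and 444 ms, the first reading is 456 ms and the average is (456 + 446 + 444)/3 = 448.7 ms, on opposite sides of the protocol's 450 ms limit. In a group of 10 to 12, one such value can set the reported maximum. Using the average at one visit and the single reading at another would also produce a mean change where none exists. ECG change is part of a named secondary safety endpoint, so the point deserves a check.

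**Working it through.** **Step 1: read the rules together.**

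| Question | Text that answers it | Answer |
|---|---|---|
| What is scheduled? | Protocol 8.2.3, Schedule of Activities | one single ECG per time point |
| What enters tables after dosing? | SAP 9 | the scheduled reading, not the repeats |
| What is baseline? | SAP 9.1 | the last scheduled predose reading |
| Are other tracings lost? | SAP 9 (Listings), SAP 15.5 | no, all are listed |
| Is averaging in tables planned? | Protocol 9.4.2 | not mentioned |

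The SAP, followed as written, applies the same rule at baseline and after dosing. No text prescribes a mixture.

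**Step 2: size of the choice.** The documents give no QTcF distribution, so these inputs are assumptions: person mean m distributed N(415, 15²); each reading = m + e with e distributed N(0, w²) and w = 5, 8 or 12 ms; entry requires one screening reading at or below 450 ms; a triplicate follows a first reading above 450 ms. With true change D, bias = E(post-dose value − baseline value) − D. Results come from 4 million simulated persons per setting. Repeating the simulation moves them by no more than a few hundredths of a millisecond.

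| Rule | D | w = 5 | w = 8 | w = 12 |
|---|---|---|---|---|
| First reading at both times | 0, 10, 20 | within 0.02 | within 0.02 | within 0.02 |
| Three new tracings averaged, both times | +10 | −0.14 | −0.35 | −0.72 |
| Same | +20 | −0.37 | −0.89 | −1.70 |
| First reading plus two averaged, both times | +10 | −0.09 | −0.24 | −0.48 |
| Same | +20 | −0.25 | −0.59 | −1.14 |
| Three new averaged, post dose only (not in the plan) | 0 | −0.04 | −0.15 | −0.49 |
| First plus two averaged, post dose only (not in the plan) | 0 | −0.03 | −0.10 | −0.33 |

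Averaging at both times has no bias at D = 0. It understates a true rise because high readings then occur more often after dosing, and only high readings are pulled back.

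**Step 3: compare with sampling error.** With 12 participants and single readings, the standard error of a mean change is w × √2/√12: 5 × 1.414/3.464 = 2.04 ms for w = 5, and 12 × 1.414/3.464 = 4.90 ms for w = 12. The largest bias in Step 2 is 1.70/4.90 = 0.35 of a standard error, and it needs a true rise of 20 ms.

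**Step 4: how often it arises.** At D = 0, 24 × 4 = 96 in-house ECGs give 0.6 to 2.5 expected QTcF triggers, with a 32% to 85% chance of at least one. Per ECG this is 0.6/96 = 0.6% to 2.5/96 = 2.6%. For one group of 12 at one time point, the chance of a trigger is 1 − (1 − 0.6/96)^12 = 7% to 1 − (1 − 2.5/96)^12 = 27%. Triplicates prompted by other ECG parameters, or taken at discretion, are not counted.

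**Step 5: maximum and SD.** In a group of 12 with a trigger, averaging three new tracings lowers the reported maximum by about 6 to 13 ms, or about 4 to 10 ms if the first reading counts as one of the three. With three new tracings the SD falls from 18.2 to 17.1 (w = 5) or from 21.2 to 18.4 (w = 12).

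**Step 6: a condition on the first-reading rule.** Exclusion criterion 14 (Protocol 5.2), which includes the 450 ms QTcF limit, names no visit, unlike criteria 12, 13, 15 and 16. If it is also applied to the Day 1 predose ECG, baseline is cut off at 450 ms. The first-reading rule then has a bias at D = 0 of about +0.04 (w = 5) to +0.48 ms (w = 12). Averaging three new tracings would give about 0.00 to +0.07 ms at D = 0, but −0.37 to −1.67 ms at a true +20 ms.

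**The case for a change.** The best case for a change is that it costs a sentence or two and removes a real silence. SAP 9 is a general rule whose example is a clotted sample, and it was plainly not written with a protocol-required triplicate in mind. Protocol 8.2.3 contains its own averaging sentence, and nothing confines that sentence to clinical review. It also leaves open whether the prompting tracing counts among the three. The trigger covers any parameter outside its reference range, so triplicates may be more frequent than the QTcF figures suggest.

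Much of this stands. The documents have no ECG replicate rule, and the protocol sentence can be read two ways. That makes the point unreconciled, but it does not show a contradiction. The sentence belongs to the assessment procedures, beside the rules on repeats and discretion, and the protocol's analysis section plans no averaging. It is therefore not shown that SAP 7 omits a departure.

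The mixed rule, the only one that creates a mean shift from nothing in the basic model, would require a programmer to set aside SAP 9 at one visit and follow it at another. Nor is there a clearly better option. The first reading leaves unconfirmed extremes in the maximum and SD. The average smooths these but pulls a genuine QTcF rise toward normal.

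**Conclusion.** No change follows. This is missing detail that the general SAP rules already fill in a sensible way, together with a fair trade-off between two acceptable values. As written, the SAP uses the scheduled single ECG at baseline and after dosing and lists every tracing.

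Under the assumed QTcF distribution, that rule biases the mean change by no more than 0.02 ms, or by about +0.04 to +0.48 ms if the predose ECG also decides eligibility. Averaging after abnormal readings would cost 0.25 to 1.70 ms at a true 20 ms rise. All of these are small beside a standard error of about 2 to 5 ms in a group of 12. The maximum and SD at a time point with a triplicate do depend on the choice, but the listings show every tracing behind them.

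The tables are descriptive, no hypothesis is tested (Protocol 9.1), SAP 15.5 plans no table of QTcF categories, and the primary PK endpoints are unaffected. The sizes rest on assumed QTcF means and SDs and on QTcF triggers alone. The reading of the text does not depend on them. A line in SAP 15.5 naming the value used would do no harm, but the analysis is sound without it.

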9.1 Definition of Baseline and Change from Baseline

If not otherwise specified, ‘baseline’ refers to the last scheduled measurement before administration of the study intervention.

However, if a participant is missing the baseline collection, the previous non-missing evaluation could become the baseline value (e.g. from screening/admission). If no baseline or previous to baseline evaluations exist, then the baseline value will be treated as missing.

Change from baseline is calculated as post-baseline visit value - baseline value.

9.2 Study Day / Study Intervention Day

Day 1 is the day of study intervention, the day before is Day -1 (no Day 0 is defined). Study day is defined relative to Day 1.

9.3 Definition of Duration and ‘Time Since’ Variables

Durations in days will be calculated by the difference of start and stop date + 1 (e.g. AE duration (days) = date of AE – date of study intervention administration + 1) if not otherwise specified.

The time since an event (e.g. relative day since first study intervention administration) will be calculated as reference date minus date of event.

9.4 Conversion Factors

The following conversion factors will be used to convert days into months or years:

1 week = 7 days, 1 month = 30.4375 days, 1 year = 365.25 days.

9.5 Imputation of Missing Data

In this Phase I PK study, missing observations will be assumed to be missing completely at random (MCAR). No action will be taken to handle missing data. A participant who withdraws prior to the

last planned observation in a study period will be included in the analyses up to the time of discontinuation.

Missing statistics, e.g. when they cannot be calculated, should be presented as “ne”. For example, if $n=1$, the measure of variability (SD) cannot be computed and should be presented as “ne”.

Incomplete AE-related dates will be imputed as follows:

- In case the onset date is missing completely or missing partially but the onset month and year, or the onset year are equal to the start of study intervention then the onset date will be imputed by the minimum of start of study intervention and AE resolution date (if not missing).
- In all other cases, the missing onset day or missing onset month will be imputed by 1.
- Incomplete stop dates will be imputed by the last day of the month (if day is missing only), if not resulting in a date later than the date of participant’s death. In the latter case, the date of death will be used to impute the incomplete stop date.
- In all other cases, the incomplete stop date will not be imputed.

There will be no imputation for missing or incomplete dates for prior or concomitant therapies.

For the derivation of previous and concomitant therapies the following rules will be applied:

Previous therapy:

- Start date \leq Start of study med OR
- Start date = Missing

Concomitant therapy:

- End date \geq Start of study med. AND (Start date \leq End of study med OR Start date=Missing) OR
- End date = Missing AND (Start date \leq End of study med. OR Start date = Missing)

The derivation is based on the following principles

- Imputation leads to max. reasonable duration
- Worst case: If medication is administered the same day as start of study medication, medication is classified as concomitant and prior

There will be no imputation for missing or incomplete dates for date of study intervention.

10 Study Participants

The subsections in this section include specifications for reporting participant disposition and study intervention/study discontinuations. Additionally, procedures for reporting protocol deviations are provided.

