**Appendices**

**Appendix 1      Abbreviations**

AE	adverse event
AESI	adverse events of special interest
ALT	alanine aminotransferase
AST	aspartate aminotransferase
CRF	case report form
CRT	chemoradiotherapy
CRU	clinical research unit
CSR	clinical study report
DLT	dose-limiting toxicity
DNA	deoxyribonucleic acid
ECG	electrocardiogram
EOT	end of study intervention
GCP	Good Clinical Practice
HIV	human immunodeficiency virus
HRT	hormone replacement therapy
IAP	Integrated Analysis Plan
IB	investigator's brochure
ICF	informed consent form
ICH	International Council for Harmonization
IEC	independent ethics committee
IMP	investigational medicinal product
IRB	institutional review board
NCI-CTCAE	National Cancer Institute Common Terminology Criteria for Adverse Events
NIMP	non-investigational medicinal product
PK	pharmacokinetic
QTcF	corrected QT interval by Fridericia' formula
RT	radiotherapy
SAE	serious adverse event
SoA	schedule of activities
SUSAR	suspected unexpected serious adverse reactions
TEAE	treatment-emergent adverse experience
ULN	upper limit of normal

---

UK	United Kingdom
----	----------------

---

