11.3 Other Baseline Characteristics

Other baseline measurements, such as serology, alcohol and drugs of abuse screen, pregnancy test and follicle-stimulating hormone assessment in women, will be listed.

Baseline characteristics with respect to vital signs, physical examinations, and hematology/biochemistry will be part of Section 15 (Safety Evaluation).

12 Previous or Concomitant Therapies/Procedures

Medications will be presented for the Safety Analysis Set.

Previous medications are defined as any medication discontinued prior to the administration of study intervention. Concomitant medications are defined as any medication taken during the course of the study, with a starting date greater than or equal to the administration of study intervention, or with a starting date prior to the administration of study intervention and ongoing at the time of the administration of study intervention.

The World Health Organization Drug dictionary (WHO-DD), Version Global Mar2022 B3 or higher, will be used for coding of previous and concomitant medications and they will be described using Preferred Term (PT) as applicable.

Previous and concomitant medications will be listed. Concomitant procedures, if any, will also be listed.

13 Study Intervention: Compliance and Exposure

Exposure to study intervention will be recorded in the eCRF. The listing of exposure to the study intervention will include the treatment, ethnic group, dose, study intervention administered and date/time of administration.

14 Efficacy Analyses

Not applicable.

15 Safety Analyses

This section includes specifications for summarizing safety endpoints that are common across clinical studies such as adverse events, laboratory tests and vital signs.

All safety analyses will be performed for the Safety Analysis Set and will be presented by ethnic group. An additional column for all ethnic groups (overall) may be presented when specified.

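### Do the conflicting previous/concomitant medication rules in SAP 9.5 and SAP 12, and the AE-duration example in SAP 9.3, require a change to the plan?

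*SAP*

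**What the plan says.** **Medication class, SAP 9.5.** Previous therapy is defined by the start date alone: on or before dosing, or missing. Concomitant therapy needs an end date on or after dosing, or a missing end date, and in both cases also "Start date \leq End of study med OR Start date=Missing". The section adds a deliberate overlap: "Worst case: If medication is administered the same day as start of study medication, medication is classified as concomitant and prior".

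**Medication class, SAP 12.** "Previous medications are defined as any medication discontinued prior to the administration of study intervention". A medication is concomitant if it is taken during the study "with a starting date greater than or equal to the administration of study intervention", or if it started earlier and was ongoing at dosing. On output the section says: "Previous and concomitant medications will be listed". It specifies no table.

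**Duration, SAP 9.3.** The rule is "Durations in days will be calculated by the difference of start and stop date + 1". The example given for it is "AE duration (days) = date of AE – date of study intervention administration + 1".

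**Context.** Protocol 4.1 gives one day of dosing. Protocol 6.8 records therapies from consent to study completion, and the Schedule of Activities reviews them up to the Day 8 contact (window -1/+2 days). The SAP does not define *End of study med*. Protocol Appendix 1 expands EOT as "end of study intervention", and the Schedule of Activities attaches that label to Day 4.

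**The concern.** An analysis plan should give a programmer one answer per record, and here two sections give different answers. Under SAP 9.5 a medication first taken on Day 2 can fall into no class, although the protocol collects such records and PK sampling runs to 72 hours. The rule also treats better data worse: a missing start with a stop on Day 3 is classed, while a known Day 2 start with the same stop may not be. Medication ongoing at dosing is both previous and concomitant in SAP 9.5 but only concomitant in SAP 12.

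In SAP 9.3 the example has no stop date. For an onset on or after Day 1 it returns the study day of onset, not how long the event lasted.

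If either variable fed a summary, an analysis set or an exclusion decision, reported results could depend on which sentence the programmer followed.

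**Working it through.** **1. Medication class.** Work on dates, with dosing on Day 1 and participation ending on the nominal Day 8. Take every known start on Days 1 to 8, crossed with every stop from the start day to Day 8 or missing. A start on Day s has (8 - s + 1) + 1 = 10 - s patterns, so the total is 9 + 8 + 7 + 6 + 5 + 4 + 3 + 2 = 44.

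- SAP 9.5 with *End of study med* = Day 1: only the 9 patterns starting on Day 1 are classed, so 44 - 9 = 35 have no class.
- SAP 9.5 with *End of study med* = Day 4: starts on Days 5 to 8 have no class, which is 5 + 4 + 3 + 2 = 14.
- SAP 12: 0 of 44 have no class.

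Typical records:

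| Record | 9.5, Day 1 reading | 9.5, Day 4 reading | SAP 12 |
|---|---|---|---|
| Start and stop before dosing | previous | previous | previous |
| Start before dosing, stop Day 3 | both | both | concomitant |
| Start and stop Day 1 | both | both | concomitant |
| Start and stop Day 2 | none | concomitant | concomitant |
| Start and stop Day 5 | none | none | concomitant |
| Start missing, stop Day 3 | both | both | not assignable |

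The Day 1 row treats SAP 12 at date level. SAP 12 refers to the act of dosing, so a medication begun and stopped on Day 1 before the dose could also count as previous there.

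**2. AE duration.** There are 8 + 7 + ... + 1 = 36 onset/stop pairs in Days 1 to 8. The rule gives stop - onset + 1. The example, with the date of the AE read as onset, gives onset - 1 + 1 = onset. The two agree only when stop = 2 × onset - 1, that is at 1/1, 2/3, 3/5 and 4/7. They disagree in 36 - 4 = 32 pairs. A one-day event on Day 8 lasts 1 day by the rule and 8 by the example; an event from Day 1 to Day 8 lasts 8 and 1. If the date of the AE is read as the stop date, they agree only for onset on Day 1 (8 pairs) and disagree in 28.

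All of these are unweighted counts of possible patterns, not expected frequencies.

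**3. Where the variables are used.**

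- SAP 9: individual listings show every record as collected, so a record with an empty class still appears.
- SAP 12: medications are listed only.
- SAP 8.1: no analysis set is defined by medication class.
- SAP 15.1: whether an event is treatment-emergent depends on its onset (or worsening) relative to dosing, not on its duration.
- SAP 15.1.1: the tables count participants and events by term, grade and relationship. None reports duration.
- SAP 16.1: PK parameters and summaries use neither variable.

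**The case for a change.** The strongest case for a change is that the contradictions are certain and a correction costs only wording. SAP 4 says the document exists to give detailed technical specifications. SAP 10.2.1 makes taking an excluded concomitant medication an important protocol deviation, allows deviations to be found by programming, and names concomitant-medication violations among events that may affect PK. On the Day 1 reading the unclassified window covers Days 2 to 4, while PK samples are still being drawn.

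The contradictions stand. The route to harm does not. No section ties a deviation check to the SAP 9.5 class. Protocol 6.8.2 identifies prohibited medication by drug and timing, and that information is in the record whatever the class. SAP 10.2.1 also relies on monitoring and medical review, requires confirmation by the Data Review Meeting at the latest, and places deviation management outside the plan. Protocol 6.8.1 and 6.8.2 permit very few medications, so few records should arise.

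Nor is rewording quite neutral. Replacing the SAP 9.5 definition of previous with that of SAP 12 would drop its missing-start branch: a record with a missing start and a stop on Day 3 would move from both classes to concomitant only. SAP 12 alone does not say how to class such a record, so the missing-date branches of SAP 9.5 still serve a purpose.

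**Conclusion.** The inconsistencies are genuine but clerical, and correcting them brings no gain in any result. SAP 9.5 reads like a general rule for repeated dosing carried into a single-dose study; SAP 12 gives the definition that fits this trial. A competent programmer would use SAP 12 for known dates, keep the SAP 9.5 handling of missing dates, and compute any AE duration from the worded rule in SAP 9.3, since the error lies only in its example.

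The largest possible effect is a class label on medication listings (35 of 44 date patterns on the Day 1 reading, 14 of 44 on the Day 4 reading) and the value of an AE-duration variable that no planned output calls for. A medication starting on Day 1 is classed under every reading.

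This rests on three assumptions: date-level comparison, participation ending on the nominal Day 8, and outputs limited to those the SAP specifies. On that basis the PK estimates, the TEAE tables, the analysis sets and the study's conclusions are the same whichever sentence is followed. No change to the plan is needed.
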